### 6.1.7 Handling of discharge and death

For the APACHE II score,

- in case a participant is discharged before Day 29 it will not be derived for any visits after the discharge visit (i.e. the last APACHE II score will be derived on the day of discharge).
- In case a participant dies no APACHE II score will be derived starting from the day of death.

### **6.1.8 Derivation of the primary estimand**

The primary estimand, referred to as the “**combined APACHE II score**”, will be derived as follows from the APACHE II scores after application of the missing data as well as discharge and death handling approaches described above:

- For participants hospitalized at Day 15: APACHE II score at Day 15
- For participants discharged prior to Day 15: APACHE II score at the discharge visit is used
- For participants that died on Day 15 or earlier: highest observed APACHE II score of any of the participants at any time during the trial
- Imputation for death takes precedence over the imputation of the APACHE II score on day of early discharge.

### **6.1.9 Supportive analysis**

Commercially Confidential Information

Commercially Confidential Information

## **6.2 Secondary objectives**

### **6.2.1 Variables**

The following variables and corresponding objectives are classified as secondary pharmacodynamic endpoints and will be evaluated for their effect of DFV890 in addition to SoC compared with SoC alone:

- On inflammatory status: Serum C-reactive protein (CRP) levels

- On clinical status: Endpoints based on the 9-point ordinal scale:
  - Survival without the need for invasive mechanical ventilation at Days 15 and 29: defined by a 9-point ordinal scale score of  $< 6$  points at all time points
  - At least one level improvement in clinical status at Days 15 and 29: defined as improvement of  $\geq 1$  in the 9-point ordinal scale score of the screening value – Day 15 or Day 29 score respectively.
  - Clinical status over time

### Missing data

For the clinical status 9-point ordinal scale missing values will be handled as follows:

- For participants who died prior to Day 29: The score for death will be imputed for all visits following the death up to and including Day 29.
- For all other participants: LOCF will be applied up to and including Day 29. Following discharge or early discharge LOCF will be applied to all intermediate visits. In case the value reported for the (early) discharge visit does not reflect that the patient is ambulatory from now on (i.e. score  $\geq 3$ ), it will be set to the highest ambulatory score i.e. a value of 2 starting from the next scheduled visit.

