### 6.1.6 Missing data

Missing data for the APACHE II score will be handled as follows:

- Missing values for age at screening will be replaced by using the stratification information assigning 3 points to participants up to 65 years ( $\leq 65$  years) and 5 points to participants above 65 years.
- Missing information on acute renal failure status: use Serum Creatinine values without renal status information.
- Subscores of the Glasgow Coma Score (i.e. responses to Best Eye Response, Motor Response, Verbal Response) scored as “untestable”, “unknown” or missing will be replaced by the last available actual score. The response “untestable” is selected if the patient is unconscious (e.g. through sedation in case of mechanical ventilation).
- Missing values in any of the other parameters required for the derivation of the APACHE II score will be replaced by the last available assessment, as long as data is not carried forward by more than 4 days.

For a given visit, these missing data rules will only be applied if for at least one of the parameters contributing to the APACHE II score a value was reported for this specific visit.

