#### Improvement in clinical status

The numbers and percentages of responders will be calculated up to Day 15 and up to Day 29 respectively. It will be presented by treatment group together with the difference in response rates.

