#### **Survival without the need for invasive mechanical ventilation**

Kaplan-Meier graphs with separate lines by treatment group will be provided for a graphical presentation. Censoring events will be death and discontinuation from the study.

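### The 9-point ordinal-scale rules conflict: LOCF without limit makes unventilated withdrawals survival responders, deaths on the landmark day can be missed, and improvement is defined at the day but counted up to it

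*SAP*

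**What the plan says.** Four places in the SAP determine how the 9-point scale becomes a response rate.

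- **Definitions (6.2.1 Variables).** Survival without invasive ventilation means a score below 6 at every time point. Improvement is tied to the day itself: "At least one level improvement in clinical status at Days 15 and 29: defined as improvement of" at least one point, taken as the screening score minus the Day 15 or Day 29 score.
- **Missing values (6.2.1, Missing data).** The death score applies as follows: "For participants who died prior to Day 29", with "The score for death will be imputed for all visits following the death up to and including Day 29". Everyone else falls under "For all other participants: LOCF will be applied up to and including Day 29". After discharge, a score of 3 or more is replaced by 2 from the next scheduled visit.
- **Tabulation (6.2.2, Improvement in clinical status).** "The numbers and percentages of responders will be calculated up to Day 15 and up to Day 29 respectively". The survival endpoint has the same sentence.
- **Graph (6.2.5, Survival without the need for invasive mechanical ventilation).** "Censoring events will be death and discontinuation from the study".

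Two other rules in the same SAP serve as comparison. For most APACHE II parameters, LOCF is allowed only "as long as data is not carried forward by more than 4 days" (6.1.6). The primary endpoint's death rule includes the landmark day: "For participants that died on Day 15 or earlier" (6.1.8).

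**The concern.** These are named secondary endpoints, reported by arm with a difference in response rates. Three things go wrong when the rules are applied literally.

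1. LOCF has no limit and no exception for withdrawal. Someone who leaves on Day 3 at score 4 is carried for 26 days (29 − 3) and enters the table as a Day 29 survivor without ventilation. The graph of the same endpoint censors that person at withdrawal. The graph also censors death, although death is score 8 (Section 10.6) and therefore a failure under the 6.2.1 definition. Table and graph do not describe the same quantity.
2. The death rule excludes a death on Day 29 itself and starts only at visits after the death. A participant who dies on Day 15 or Day 29 with no score entered that day keeps the last living score at that visit.
3. The definition of improvement and the sentence that tabulates it point to different counts. Someone who improves and later worsens or dies could be classed either way, so two programmers could report different rates.

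**Working it through.** **Inputs.** The rules are those of SAP 6.2.1, 6.2.2 and 6.2.5, with visits every 2 days (Section 1.4). The visible SAP gives no sample size, withdrawal rate or event rate for these endpoints, so there is no planned figure to reproduce. All rates below are assumptions.

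**Step 1: apply the rules literally to hypothetical participants, all starting at score 5.**

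| Course | Survival without ventilation, Day 15 / Day 29 | Improvement on the day, Day 15 / Day 29 | Improvement at any time up to the day |
|---|---|---|---|
| Withdraws Day 3, still 5 | yes / yes | no / no | no / no |
| Withdraws Day 3, at 4 | yes / yes | yes / yes | yes / yes |
| Score 6 on Day 3, withdraws Day 5 | no / no | no / no | no / no |
| Dies Day 28 | yes / no | no / no | no / no |
| Dies Day 29, no score entered | yes / **yes** | no / no | no / no |
| Dies Day 29, score 8 entered | yes / no | no / no | no / no |
| Dies Day 15, no score entered | **yes** / no | no / no | no / no |
| Score 4 on Day 5 only, then back to 5 | yes / yes | no / no | **yes / yes** |
| Score 4 on Day 5, score 6 from Day 11 | no / no | no / no | **yes / yes** |

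**Step 2: size of the LOCF effect on the survival rate.** Let w be the share of an arm that withdraws with all scores below 6, and q the probability that such a participant is ventilated or dies unobserved by the landmark day. LOCF counts all of w as success, while the true contribution is w(1 − q). Overstatement = w × q.

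- w = 5%, q = 30%: 0.05 × 0.30 = 1.5 points.
- w = 10%, q = 30%: 0.10 × 0.30 = 3 points.
- For q from 0.2 to 1.0: 1 to 5 points at w = 5%, 2 to 10 at w = 10%, 3 to 15 at w = 15%.

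The error in the between-arm difference is w × q in one arm minus w × q in the other. It is zero when the products are equal.

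**Step 3: compare ways of handling withdrawals.** Assume 80% success among those followed and q = 30%. If all withdrawals precede the first event, Kaplan-Meier with withdrawal censored gives the rate among those followed, 80%.

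| | w = 5% | w = 10% |
|---|---|---|
| True rate, (1 − w) × 80% + w × 70% | 79.5% | 79% |
| LOCF, (1 − w) × 80% + w | 81% (+1.5) | 82% (+3) |
| Non-responder, (1 − w) × 80% | 76% (−3.5) | 72% (−7) |
| Kaplan-Meier, withdrawal censored | 80% (+0.5) | 80% (+1) |

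Under these assumptions Kaplan-Meier has the smallest error, and counting every withdrawal as a failure errs more than LOCF does.

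**The case against.** The strongest reply is that the rules misclassify less than they seem to, and much of it stands.

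- A reader might infer that failures are being counted as successes. The documents do not support that for withdrawals: their outcome is unknown, and anyone already at 6 or above stays a failure.
- A reader might infer that both response rates are inflated. For improvement, LOCF can err either way, because a participant who withdraws unimproved is carried as a non-responder.
- A reader might infer that an any-time rule has replaced the improvement definition. It has not: 6.2.1 still fixes the score on the day, and the 6.2.2 sentence may simply be repeated from the survival endpoint, where it fits. What is shown is a contradiction.
- The death-day gap needs a death exactly on Day 15 or Day 29 with no score entered. A recorded 8 needs no imputation. The gap is rare, though plausible for a discharged participant whose Day 29 visit is a telephone call.
- Discharged participants have Day 15 and Day 29 contacts, LOCF values are marked on the heat map, and discontinuations are tabulated by reason. The long carry-forward therefore mainly concerns study withdrawals.

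None of this removes the unlimited carry-forward, the conflict between table and graph, or the two wording defects. The heat-map marking does not alter the response rates.

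**Conclusion.** The point holds as a set of conflicting rules that can misclassify participants in descriptive secondary results. In the visible text no test is attached to these response rates, and the primary analysis does not use them.

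The main item is LOCF to Day 29 for withdrawals. It overstates survival without invasive ventilation by w × q, which is 1.5 to 3 points at an assumed 5% to 10% withdrawal with 30% unobserved events, and more if either share is higher. The open-label design makes unequal withdrawal possible, and a reader might infer that the treatment difference is therefore biased. That follows only if w × q differs between arms, and the SAP gives no figures to show it.

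The death-day wording is a rare edge case. The improvement wording leaves the count undetermined for anyone who improves and then worsens or dies; its size depends on how many do so, which the SAP does not give.

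**What to change.** 1. **Survival without invasive ventilation.** Report the Day 15 and Day 29 rates and their difference from Kaplan-Meier estimates, with death or a score of 6 or more as the event and study withdrawal censored. Amend 6.2.5 so that death is no longer censored. This assumes withdrawals carry the same risk as those who stay, so the SAP should say so. Withdrawals as non-responders can be added as a sensitivity analysis, but not as the main rule.
2. **LOCF (6.2.1, Missing data).** Keep it for discharged participants and for isolated missed visits followed by an observed score, so that one missed assessment does not fail a hospitalised participant. Withdrawn participants then have no Day 15 or Day 29 score for improvement, and the SAP should state how they are shown in that table.
3. **Death rule.** Word it as death on or before Day 29, with score 8 from the day of death.
4. **Improvement (6.2.2).** Replace *up to* by *at*, to match the definition in 6.2.1. The survival sentence can keep *up to*, since that endpoint covers all time points.

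The cost is an SAP wording change and a small programming change. Reported survival rates would be slightly lower: in the example above, 80% instead of 81% or 82%.

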## 10.6 9-point ordinal scale

Patient State	Descriptor	Score	Abbreviated description
Uninfected	No Clinical or virological evidence of infection	0	Uninfected
Ambulatory	No limitation of activities	1	Amb: No limitations
	Limitation of activities	2	Amb: Limitations
Hospitalized Mild disease	Hospitalized, no oxygen therapy	3	Hosp: No Oxygen
	Oxygen by mask or nasal prongs	4	Hosp: Oxy Mask
	Non-invasive ventilation or high-flow oxygen	5	Hosp: Non-Inv Vent
Hospitalized Severe disease	Intubation and mechanical ventilation	6	Hosp: Intub + Mech Vent
	Ventilation + additional organ support - pressors, RRT, ECMO	7	Hosp: Vent + pressors
Dead	Death	8	Dead

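### The post-discharge reset of the 9-point score to 2 has no upper limit, so a participant recorded as leaving with a score of 5 to 7 and not scored again counts as ambulatory and improved

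*SAP*

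**What the plan says.** SAP 6.2.1, under Missing data, sets out how gaps in the 9-point scale are filled. A participant who has died gets the death score up to Day 29. For everyone else, "LOCF will be applied up to and including Day 29". For participants who have left hospital, "Following discharge or early discharge LOCF will be applied to all intermediate visits".

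An exception then follows. "In case the value reported for the (early) discharge visit does not reflect that the patient is ambulatory from now on", which the SAP spells out as a score of 3 or more, "it will be set to the highest ambulatory score i.e. a value of 2 starting from the next scheduled visit". A score of 3 or more is the only condition. There is no upper bound, and nothing is said about where the participant went.

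The scale is in SAP 10.6. Scores 3 to 7 are all hospitalized states. Score 5 is high-flow oxygen or non-invasive ventilation, score 6 is "Intubation and mechanical ventilation", and score 7 adds further organ support. Score 2 is ambulatory with limited activities.

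SAP 6.2.1 (Variables) lists "At least one level improvement in clinical status at Days 15 and 29" as a secondary endpoint. It is met when the screening score minus the Day 15 or Day 29 score is at least 1.

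**The concern.** The reset has a sensible purpose. A score recorded on the day of discharge may still describe the hospital stay, and carrying a 3 or 4 forward for someone now at home would be wrong. That reasoning fits scores 3 and 4. It does not fit a participant recorded as discharged while on high-flow support or intubated. There the recorded score is evidence of severe illness, and the rule replaces it with an ambulatory state without any information that the participant recovered.

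One route to such a record is a transfer to another hospital, if transfers are entered as discharges. Another is a data error. In either case, when no later score is obtained, a recorded severe or worsened status is counted as a success at the days on which the endpoint is read. The trial is open label (SAP 1.4), so there is no assurance that such cases would balance between the arms.

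**Working it through.** The SAP states no figure on this point, so there is none to reproduce. The check applies the written rule to possible participants.

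**Inputs**
- Reset: a discharge-visit score d of 3 or more becomes 2 from the next scheduled visit (SAP 6.2.1, Missing data).
- Improvement: s - x ≥ 1, where s is the screening score and x the Day 15 or Day 29 score (SAP 6.2.1, Variables).
- Hospitalized scores: 3 to 7 (SAP 10.6).
- Assumptions: s lies between 3 and 7, as the SAP does not state the eligible ordinal range; discharge precedes the reading day; no score is observed on that day.

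**One participant.** Take s = 5 and d = 6.
- Reported score carried forward: 5 - 6 = -1, one level worse, not a responder.
- Rule as written: 5 - 2 = 3, a three-level improvement, a responder.

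**All pairs of s and d**

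| Screening s | Discharge d | Pairs | Improved, d carried | Improved, reset to 2 |
|---|---|---|---|---|
| 3-7 | 3-4 | 10 | 7 | 10 |
| 3-7 | 5-7 | 15 | 3 | 15 |
| 4-5 | 5-7 | 6 | 0 | 6 |

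After the reset every pair is improved, because s - 2 ≥ 1 for any s of 3 or more. For d of 5 to 7 with d carried, only three pairs improve: (s, d) = (6, 5), (7, 5) and (7, 6). The reset therefore changes the result in 15 - 3 = 12 of 15 pairs, and in 6 of 6 if screening scores are limited to 4 and 5. These are unweighted counts of possible combinations. They show what the rule does, not how often it happens.

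**Effect on an arm of n participants.** Each misclassified participant raises the responder rate by 1/n. On the mean score reported by visit, each lowers the arm's mean by (d - 2)/n: 3/n for d = 5, 4/n for d = 6 and 5/n for d = 7.

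**Ventilation-free survival.** This requires a score below 6 at all time points. The reset starts at the visit after discharge, so a recorded 6 or 7 stays at the discharge visit and the participant fails. With d = 5, both the reset value 2 and the carried value 5 are below 6, so the choice between them does not change this endpoint.

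**The case against.** The strongest reply is that the rule fills missing values only. SAP 1.4 has participants discharged early return for a Day 15 assessment, with home nursing as a back-up where available, and adds a Day 29 telephone visit. On a natural reading, scores obtained there stand. This is right and it narrows the point: the reset decides the endpoint only when the planned contact gives no score. The precedence is implied, however, not written.

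Second, the SAP does not say that anyone leaves with a score of 5 to 7, or whether a transfer counts as a discharge. That definition may sit in the protocol. A reader might infer that critically ill participants moved to other hospitals will be counted as improvers. The SAP supports this only conditionally: they must be recorded as discharged and have no later score. Known deaths are covered by their own rule.

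Third, the analyses concerned are descriptive. SAP 6.2.2 gives counts, percentages and a difference for improvement. Its heat map flags discharge and marks carried-forward values, so a careful reader could see some of these cases. That helps with the plot but does not correct the responder rate.

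A reader might also infer that the start at the next scheduled visit is an error, because a participant discharged on Day 15 or Day 29 keeps a hospitalized score on that day. The SAP does not support this. Such a participant was in hospital that day and has an observed score, and keeping it is an acceptable convention. The contrast with a discharge shortly before Day 15 arises only if the planned Day 15 visit yields no score. Nor is there a stated reason for discharges to cluster on Day 15, since treatment continues at home after an earlier discharge.

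**Conclusion.** The point holds for the missing upper limit. As written, the rule converts any discharge-visit score of 5 to 7 into ambulatory status and, for any screening score of 3 or more, into an improvement, provided no later score is obtained. For screening 5 and discharge score 6 the error is four levels, from -1 to +3.

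The improvement responder rate, the Day 15 and Day 29 bar charts and clinical status over time are affected. The primary endpoint is not touched, and ventilation-free survival is not rescued where a 6 or 7 was recorded. The size in the trial is 1/n per affected participant. The number affected is not given and may be small or zero. The conclusion rests on the literal wording, on such participants being recorded as discharged, and on the later contact being missing.

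**What to change.** Amend the Missing data rule in SAP 6.2.1 before database lock:

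1. Limit the reset to discharge-visit scores of 3 and 4, starting at the next scheduled visit as now.
2. For discharge-visit scores of 5 to 7, or a known transfer to another acute hospital, carry the reported score forward unless discharge home is confirmed.
3. State that a score observed at the Day 15 visit or the Day 29 call takes precedence over any imputed value.

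The handling of a discharge on Day 15 or Day 29 itself can stay as it is.

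The cost is a few sentences and a small programming change. Discharge destination can be used where it was collected; otherwise the score threshold is enough. The small downside is that some of these participants carry a severe score until the next contact, even if they improved in the meantime.

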### 6.2.2 Descriptive analyses

#### CRP

Panels of individual spaghetti plots over time for CRP will be provided using a logscale. The profiles of all participants in the respective treatment group will be included in these graphs as grey lines in the background and the respective individual participants profile will be plotted with darker color in the foreground. The respective applicable normal ranges will be added and it will be indicated by a symbol if a patient died.

#### Survival without the need for invasive mechanical ventilation

The numbers and percentages of responders will be calculated up to Day 15 and up to Day 29 respectively. It will be presented by treatment group together with the difference in response rates.

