### 1.3 Study objectives

**Table 1-1 Study objectives**

Objective(s)	Endpoint(s)
Primary Objective(s) 
 
To evaluate the effect of DFV890 in addition to SoC, compared with SoC alone, on the Acute Physiology and Chronic Health Evaluation II (APACHE II) score
 
	Endpoint(s) for primary objective(s) 
 
APACHE II severity of disease score on Day 15 or on day of discharge (whichever is earlier) with worst case imputation for death
 

Secondary Objective(s) 
 
To evaluate the effect of DFV890 in addition to SoC, compared with SoC alone, on inflammatory status
 
To evaluate the effect of DFV890 in addition to SoC, compared with SoC alone, on clinical status
 
	Endpoint(s) for secondary objective(s) 
 
Serum C-reactive protein (CRP) levels
 
 Endpoints based on the 9-point ordinal scale: 
 
Survival without the need for invasive mechanical ventilation at Days 15 and 29
 
At least one level improvement in clinical status at Days 15 and 29
 
Clinical status over time
 

 
To evaluate the safety of DFV890 in addition to SoC, compared with SoC alone
 
	
 
Number of participants with Adverse Events (AE), Serious Adverse Events (SAE), clinically significant changes in laboratory measures, and vital signs
 

Commercially Confidential Information

[figure not shown]

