### 6.1.3 Statistical model, assumptions and hypotheses

The combined APACHE II endpoint as described in the estimand above is assumed to follow a normal distribution.

The primary endpoint will be analyzed by an analysis of covariance model including treatment group and the three stratification factors as factors and baseline APACHE II score as a covariate. The analysis will be performed on the safety analysis set. The mean differences of DFV890 in addition to SoC vs SoC alone will be reported with 90% confidence intervals (CIs). The 1-sided p-value for the overall treatment factor will be reported.

The primary objective will be achieved if the null hypothesis that DFV890 in addition to SoC is not different to SoC alone is rejected using a one side alpha of 10%.

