### **6.2.3 Statistical model, assumptions and hypotheses**

#### **CRP**

CRP levels are assumed to follow a log-normal distribution. Thus the log-transformed CRP data will be analyzed by fitting an MMRM model. Treatment, visit and their interaction as well as the three stratification factors will be included as fixed factors and log-transformed baseline CRP as a covariate. Interactions between visit and each of the terms in the model will also be included. To model the dependency of observations an unstructured variance-covariance matrix will be fitted.

The analysis will be performed on the PD analysis set. All available values at all scheduled visits (excluding discharge or early discharge visits) up to Day 29 will be included in this analysis. The back-transformed geometric means for both treatment groups as well as the geometric mean ratios (DFV890 in addition to SoC vs SoC alone) will be reported together with 90% confidence intervals (CIs) for each visit. The 1-sided p-value for the overall treatment factor will be reported.

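### The difference in response rates for the two binary clinical-status endpoints has no confidence interval and no adjustment for strata or baseline, unlike the primary endpoint and CRP

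*SAP*

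**What the plan says.** SAP Table 1-1 makes clinical status a comparative secondary objective: "To evaluate the effect of DFV890 in addition to SoC, compared with SoC alone, on clinical status". Two of its endpoints are binary, each assessed at Days 15 and 29:

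- Ventilation-free survival, which section 6.2.1 introduces as "Survival without the need for invasive mechanical ventilation at Days 15 and 29: defined by a 9-point ordinal scale score of" less than 6 throughout.
- Improvement by at least one level, which is the screening score minus the Day 15 or Day 29 score.

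Section 6.2.2 gives both the same numerical plan: "The numbers and percentages of responders will be calculated up to Day 15 and up to Day 29 respectively", followed by "It will be presented by treatment group together with the difference in response rates".

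Section 6.2.3, the model section for secondary objectives, covers CRP alone. There, "the three stratification factors will be included as fixed factors and log-transformed baseline CRP as a covariate", and the results "will be reported together with 90% confidence intervals (CIs) for each visit". For the primary endpoint, section 6.1.3 sets an ANCOVA "including treatment group and the three stratification factors as factors and baseline APACHE II score as a covariate", also with 90% intervals.

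Section 6.2.5 adds a Kaplan-Meier graph for ventilation-free survival, and section 6.2.2 adds summaries, bar charts and heat maps of the ordinal scale. No interval, test or model is attached to any of these. No redaction mark appears in the shown text of 6.2.2, 6.2.3 or 6.2.5.

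**The concern.** A difference in response rates between randomised arms is an effect estimate. These two endpoints are the plan's most direct measures of how patients fare, yet they get a point estimate without a statement of precision. CRP, a secondary endpoint of equal rank, gets an adjusted estimate and an interval.

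Two things are at stake. First, a difference of 5 or 10 points will appear in the report with nothing beside it to show how far it could be from the true value. Second, the baseline 9-point score is likely to predict both endpoints, and the strata were chosen for randomisation. Leaving them out of these two comparisons leaves any chance imbalance in the estimate and may give up some precision. If the interval and the adjustment are not fixed beforehand, they will be chosen after the data are known, in an open-label trial.

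**Working it through.** **1. The planned analyses side by side**

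| Endpoint | Section | Strata in comparison | Baseline covariate | Interval |
|---|---|---|---|---|
| Combined APACHE II score (primary) | 6.1.3 | yes | APACHE II | 90% |
| CRP (secondary) | 6.2.3 | yes | log CRP | 90% |
| Ventilation-free survival (secondary) | 6.2.2 | no | none | none |
| Improvement of at least one level (secondary) | 6.2.2 | no | none | none |

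The data for adjustment already exist. Section 7.2.1 tabulates the baseline 9-point score and the three stratification factors by arm.

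**2. Whether the Kaplan-Meier graph fills the gap**

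It does not. It covers one of the two endpoints and has no interval or test. Section 6.2.5 also censors death, whereas the binary endpoint counts death as failure, because death scores 8 (section 10.6) and the endpoint requires a score below 6. The graph and the responder difference therefore describe different quantities.

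**3. Scale of the missing interval**

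The SAP text shown states no sample size and no response rate for these endpoints, so there is no figure of its own to reproduce. Arm size n and the rates below are assumptions. The 1:1 allocation (section 1.4) and the 90% level (sections 6.1.3 and 6.2.3) come from the SAP.

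Wald half-width = 1.645 × √[p1(1−p1)/n + p2(1−p2)/n].

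Worked case, n = 70, 75% v 65%: √(0.1875/70 + 0.2275/70) = √0.005929 = 0.0770; × 1.645 = 0.127, or 12.7 points.

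| n per arm | 85% v 80% | 75% v 65% |
|---|---|---|
| 50 | ±12.5 | ±15.0 |
| 60 | ±11.4 | ±13.7 |
| 70 | ±10.5 | ±12.7 |
| 100 | ±8.8 | ±10.6 |

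In every cell the half-width exceeds the difference itself (5 or 10 points).

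**4. What the report would show with an interval**

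Take an observed 80% v 70%, with the unadjusted Newcombe 90% interval. The last column is the one-sided p from the pooled z statistic, z = 0.10/√[2 × 0.75 × 0.25/n].

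| n per arm | Newcombe 90% interval (points) | one-sided p |
|---|---|---|
| 30 | −8 to +28 | 0.19 |
| 50 | −4 to +24 | 0.12 |
| 70 | −2 to +22 | 0.09 |
| 100 | −0.1 to +20 | 0.05 |

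The p-values are for scale only. The same 10-point difference falls on either side of 10%, the one-sided level set for the primary test, depending on arm size.

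**5. What cannot be computed**

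An adjusted interval needs stratum sizes, rates within strata and the association of baseline score with outcome. The SAP gives none of these, so the gain from adjustment has no figure here.

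**The case against.** The strongest reply is that this is a deliberate and legitimate choice. The text sits under a heading for descriptive analyses. The model and model-checking sections consistently confine themselves to CRP, and the only success criterion is the primary test. Describing secondary endpoints in an open-label Phase 2 trial is common. The objective's wording does not demand a model either: the safety objective is also framed as a comparison with SoC, and its visible analyses are descriptive. All of this stands, and it is why no formal test is asked for. It does not remove the case for an interval, which states precision and is not a test.

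A reader might infer several stronger things that the document does not support:

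- *That the plan leaves no way to judge whether a difference could be chance.* Counts and percentages by arm are reported, and a crude interval needs nothing more.
- *That the raw difference is the sole output.* Kaplan-Meier curves and by-visit ordinal summaries are also planned, although they carry no precision.
- *That the strata and baseline score go unused.* The screening score defines the improvement endpoint, both are tabulated at baseline, and the strata enter the APACHE II and CRP models. They are absent as covariates for these two endpoints, and no more than that.
- *That a measurable amount of precision is being lost.* No figure can be put on it.

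Sections 6.1.9 and 6.3 are redacted and the protocol is not at hand, so a further analysis of these endpoints elsewhere cannot be excluded. Section 6.2, where it would belong, shows none.

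**Conclusion.** The point holds as an avoidable weakness, not as an error or contradiction. For both binary endpoints at Days 15 and 29, the SAP plans a between-arm difference without an interval and without adjustment, out of line with its own practice for the primary endpoint and CRP. The missing interval is the firmer half: under the assumed 50 to 100 per arm and the two assumed rate pairs, it hides a 90% half-width of about 9 to 15 points. The adjustment half rests on consistency and general principle, because its benefit cannot be sized from the document.

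A reader might go further and conclude that the trial's main result is compromised or that a hypothesis test is owed. Neither follows. The primary analysis does not depend on these endpoints, and a descriptive role for them is acceptable. This is a free improvement and should be made before database lock.

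**What to change.** Amend sections 6.2.2 and 6.2.3 so that, for both endpoints at Days 15 and 29, the difference in response rates is reported as follows:

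1. **Estimator.** Logistic regression with treatment, the three stratification factors and baseline 9-point score, standardised over all analysed participants to give a risk difference.
2. **Interval.** A 90% confidence interval, matching the level used for APACHE II and CRP.
3. **Fallback.** If the model does not converge or shows separation, report the unadjusted difference with a Newcombe 90% interval and say so. This trigger is defined in advance and leaves no choice between estimators once the data are seen.
4. **Status.** State that the interval is for estimation and that no formal test is made.

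The same text should name the analysis set for these two endpoints. Section 6.1.3 does so for the primary endpoint and section 6.2.3 does so for CRP, but the shown text of 6.2.2 does not.

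One named model is preferable to Mantel-Haenszel weighting here, since crossing three stratification factors with a multi-level baseline score could leave thin strata.

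The cost is a few lines of SAP text and standard programming. No new data are needed, and the primary test is untouched.
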